4.1.2 Enrollment/Baseline

Eligible caregivers who provide consent via REDCap will be presented with the baseline survey queue on REDCap. The baseline forms are expected to take about

45 minutes to complete. Once study staff receive complete baseline forms, participants will be randomly assigned to either IRC or R2R-TBI and will be sent a link, password, and instructions on how to access the R2R-TBI application or IRC website.

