5.1 Statistical and Analytical Plans

Caregiver functioning is examined as the primary and most proximal outcomes of the R2R-TBI intervention. Through targeting caregiver functioning, we expect the R2R-TBI intervention to have downstream effects (through reductions in caregiver depression and distress) on the secondary outcomes of child recovery and family functioning. We further anticipate that the same risk and protective factors that have been shown to moderate child recovery and the efficacy of other family-centered interventions for pediatric TBI, such as household income and baseline family functioning, will moderate the efficacy of the R2R-TBI intervention (e.g., Antonini et al., 2014; Raj et al., 2014b; Wade et al., 2012, 2015). Specifically, we anticipate that the R2R-TBI intervention will be most effective among low-income families and among caregivers with high levels of baseline distress. Our hypotheses are as follows:

Hypothesis 1: Caregivers receiving the R2R-TBI intervention will report lower levels of depression, anxiety, post-traumatic stress, and higher levels of caregiver self-efficacy and mindful self-care at follow-up, compared to caregivers in the IRC condition, after controlling for baseline levels.

The R2R-TBI intervention is designed to promote caregiver psychological well-being and positive parenting in the acute phase post-injury. This hypothesis represents an important test of whether the intervention is successful in improving these areas of functioning that are targets of the intervention. To evaluate this hypothesis, we will examine group difference in caregiver depression (CES-D-10, Radloff, 1977), anxiety (PROMIS Anxiety 4a), post traumatic stress (PC-PTSD-5, Prins et al., 2015), caregiver self-efficacy (CSES, Boothroyd & Evans, 1997), and mindful self-care (MSCS-25; Cook-Cottone, 2015) at one and six-months post-baseline, controlling for baseline scores. Given the challenges in the acute phase post-injury, we expect caregivers in the R2R intervention to report stable functioning while caregivers in the IRC group to report increasing levels of depression and distress at both one and six-month follow-ups.

Hypothesis 2: Caregivers receiving the R2R intervention will report better child and family functioning at follow-up, compared to caregivers in the IRC condition, after controlling for baseline functioning.

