We anticipate that the R2R-TBI intervention will be effective in both ameliorating problems evident at baseline and in preventing emergence of additional problems in family and child functioning at one and six-months post-baseline. To test this hypothesis, we will examine group differences in family functioning (FAD-GF, Epstein, Baldwin, & Bishop, 1983), family burden of injury (FBI, Burgess et al., 1999) and child socioemotional functioning (PedSQL Psychosocial Summary Score, Varni et al., 1999) at one and six-months post-baseline.

Hypothesis 3: We hypothesize that treatment effects will be moderated by household income and level of caregiver distress at baseline.

We expect families with greater social disadvantage (lower income, more stress) will benefit most from the R2R-TBI intervention. This hypothesis is consistent with previous research findings (e.g., Antonini et al., 2014; Raj et al., 2014b; Wade et al., 2012, 2015).

Variable distributions will be examined before carrying out inferential statistical procedures, and transformations will be made in cases where distributions are skewed or fail to meet the assumptions of normality. Non-parametric procedures will be employed in cases where transformations would be inappropriate or where analysis of frequencies is justified. Preliminary work will also involve computation of reliabilities and creation of derived variables that summarize performance on measures that are highly inter-correlated. To evaluate potential attrition bias, caregivers who drop out (i.e., those who access < 3 modules and/or who do not complete baseline or follow-up measures) will be compared to those who remain in follow-up on background characteristics as well as on outcomes measured prior to dropout. Factors related to dropout will be included as covariates in the analysis.

Analytic plan for hypotheses 1 and 2. The primary analysis will consist of a linear mixed-effect models used to examine changes in caregiver, family, and child functioning among participants in the R2R-TBI intervention and IRC groups from baseline to 6-months post-baseline. In addition, the one-month data will be included in a mixed model repeated measures analysis. This model allows for flexible modeling of the pattern of change in outcomes over time and uses all the data for a given participant, even if that participant is not seen at all assessments, allowing us to retain participants with missing assessments.

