Analytic plan for hypothesis 3. Existing literature and findings from our other studies suggest that demographic factors such as household income as well as baseline caregiver functioning impact adaptation to injury, and we hypothesize that these factors will moderate the efficacy of the intervention. Hierarchical multiple regression analyses which include the interaction of group, moderator (household income, baseline functioning), and time in the model will be used to test hypothesis 3. Variable selection using backward elimination will be used to remove non-significant higher- and then lower-order terms. In order to avoid selection bias, bootstrapping will be used on the backward elimination process (Austin, 2008). Post hoc analyses will be used to compare

treatment groups on each outcome at different levels of the moderators at 1 and 6-months post-baseline.

6. Data Management

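### The primary model for Hypotheses 1 and 2 should build in the baseline adjustment they promise: with baseline as an unconstrained response, the test gives up (1 − ρ)/2 of the effective sample

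*Combined protocol and SAP*

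**What the plan says.** Everything relevant is in section 5.1 of the combined protocol and SAP, except the order of baseline and randomisation.

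- **Hypothesis 1** is to be evaluated by group differences "at one and six-months post-baseline, controlling for baseline scores".
- **Hypothesis 2** is that R2R-TBI caregivers "will report better child and family functioning at follow-up, compared to caregivers in the IRC condition, after controlling for baseline functioning".
- **The model for both:** "The primary analysis will consist of a linear mixed-effect models used to examine changes in caregiver, family, and child functioning", covering the period "from baseline to 6-months post-baseline". It continues: "In addition, the one-month data will be included in a mixed model repeated measures analysis".
- **Covariates** named in the modelling text: "Factors related to dropout will be included as covariates in the analysis". The baseline score of the outcome is not listed.
- **Hypothesis 3** uses the "interaction of group, moderator (household income, baseline functioning), and time in the model". Its post hoc comparisons are placed at 1 and 6 months.
- **Timing** (section 4.1.2): "Once study staff receive complete baseline forms, participants will be randomly assigned".

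The plan does not give the fixed effects, the covariance structure, any constraint on baseline means, or the contrast that is the test.

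**The concern.** The hypotheses describe an adjusted comparison of follow-up scores. The model paragraph describes an analysis of change. The two are not interchangeable in precision. In a mixed model with baseline among the responses and a separate baseline mean for each arm, the group-by-time term reproduces the difference in mean change. Subtracting the whole baseline score over-corrects whenever ρ is below 1. It adds noise, and it carries (1 − ρ) of any chance baseline gap into the estimate.

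Enrolment is capped at 200 (section 3.5), so lost precision cannot be recovered by recruiting more. The issue touches every outcome under Hypotheses 1 and 2.

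**Working it through.** **Which reading fits the text.** The 1-month data enter through an additional analysis, so the first model uses baseline and 6 months. If baseline were only a covariate there, each caregiver would supply one response, and a mixed model would have no repeated measure to work on; no other clustering factor is named. Baseline as a response is therefore the most natural reading. Nothing in the text sets the arm means equal at baseline.

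**Inputs.**
- Up to 200 caregivers with equal allocation probabilities (section 3.5); taken as 100 per arm with no dropout.
- ρ is not given; assumed over 0.2 to 0.9.
- Equal SD at baseline and follow-up, complete data: assumed. Results are in SD units.
- Two-sided 5% and 80% power: assumed, and used only for the detectable differences.

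The plan gives no power calculation, so there is no stated figure to reproduce.

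**Formulas.** Let D0 and D1 be the arm differences in means at baseline and at follow-up.
- Difference in change: D1 − D0, with variance (2/100) × 2(1 − ρ).
- Baseline-adjusted difference: D1 − ρD0, with variance (2/100) × (1 − ρ²).
- Relative efficiency: (1 − ρ²) / [2(1 − ρ)] = (1 + ρ)/2, so the loss is (1 − ρ)/2.
- Ratio of standard errors: √[2/(1 + ρ)].
- Detectable difference: (1.96 + 0.84) × √(2 × variance factor / 100).

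| ρ | Factor, change | Factor, adjusted | Loss | 200 act like | SE ratio | Detectable, change | Detectable, adjusted |
|---|---|---|---|---|---|---|---|
| 0.2 | 1.60 | 0.96 | 40% | 120 | 1.29 | 0.50 | 0.39 |
| 0.4 | 1.20 | 0.84 | 30% | 140 | 1.20 | 0.43 | 0.36 |
| 0.5 | 1.00 | 0.75 | 25% | 150 | 1.15 | 0.40 | 0.34 |
| 0.6 | 0.80 | 0.64 | 20% | 160 | 1.12 | 0.35 | 0.32 |
| 0.7 | 0.60 | 0.51 | 15% | 170 | 1.08 | 0.31 | 0.28 |
| 0.9 | 0.20 | 0.19 | 5% | 190 | 1.03 | 0.18 | 0.17 |

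A comparison of follow-up scores that ignores baseline has factor 1. Below ρ = 0.5, then, the change analysis is less precise than not using baseline at all.

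**Check with three visits.** Generalised least squares with baseline, 1 and 6 months, compound symmetry and 100 per arm gives these variance factors for the 6-month effect at ρ = 0.4, 0.5, 0.6 and 0.7:
- free baseline means: 1.20, 1.00, 0.80, 0.60, the same as the change score;
- common baseline mean: 0.84, 0.75, 0.64, 0.51, the same as the adjusted analysis.

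Adding the 1-month visit does not recover the loss. Constraining the baseline means removes it entirely.

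**Chance imbalance.** The standard error of D0 is √(2/100) = 0.14 SD. A gap of that size at ρ = 0.5 moves the change estimate away from the adjusted one by (1 − 0.5) × 0.14 = 0.07 SD. The adjusted standard error is √(2 × 0.75/100) = 0.12 SD.

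**The case against.** The best reply is that section 5.1 should be read as a whole. The hypotheses say that baseline is controlled for, the model paragraph never calls baseline a response, and an analyst could carry the adjustment into the model as a covariate or a constraint. On that reading nothing is lost. This stands to a point: the text does not prove a contradiction, and the loss is conditional on free baseline means. But the paragraph's own wording leans the other way, and it leaves non-equivalent models open for every outcome.

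Four stronger conclusions might be inferred. The documents do not support them.

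- **That the model estimates a different effect or is biased.** Under randomisation the difference in change and the adjusted difference target the same average effect. The cost is in precision and chance imbalance.
- **That a fixed share of the sample is wasted.** The share depends on ρ, which the documents do not give.
- **That error bars would be wrong if baseline were both response and covariate.** In simulations with 200 caregivers and ρ from 0.3 to 0.6, type I error of about 6 to 8% appeared only in a two-visit fit that could not allow negative within-person covariance. With that covariance allowed it was 4 to 6%. With three visits and a random intercept, the ratio of reported to true standard error was 0.996 at ρ = 0.4 and 0.999 at ρ = 0.6. The plan specifies no covariance structure, so no general claim follows.
- **That Hypothesis 3 puts baseline functioning on both sides of the model.** This holds only if time there includes baseline, and the plan's own post hoc comparisons at 1 and 6 months point the other way.

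**Conclusion.** The point holds as a free improvement: a more precise analysis of data already being collected, and one that matches what the hypotheses promise. On the most natural reading of the model paragraph, with free baseline means, the primary test loses (1 − ρ)/2 of the effective sample. For an assumed ρ of 0.4 to 0.7, 200 caregivers would give the precision of about 140 to 170 analysed with adjustment, and standard errors would be 1.20 to 1.08 times as large. These figures rest on equal variances, complete data and 100 per arm. If the baseline means are constrained equal, or baseline is a covariate with follow-up scores as the only responses, the loss is zero.

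**What to change.** Replace the primary-model sentence in section 5.1 with one model per outcome:

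- **Responses:** the 1- and 6-month scores.
- **Fixed effects:** arm, visit, arm × visit, baseline score, baseline × visit.
- **Covariance:** unstructured within caregiver.
- **Report:** the adjusted R2R-TBI minus IRC difference at each visit.

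A model that keeps baseline as a response with arm means constrained equal at baseline is an acceptable equivalent. Choose one, and do not enter baseline as both response and covariate. For Hypothesis 3, state that time means the 1- and 6-month visits.

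The cost is SAP wording only. Because randomisation follows receipt of complete baseline forms, conditioning on baseline should lose no caregiver who has a follow-up score. A caregiver with only one of the two follow-ups still contributes, so the plan's aim of retaining participants with missed assessments is kept.

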If the parent or individual is not interested, they will be thanked for their time and no further contact about the study will be made. If interest in the study is expressed, the parent will be sent a link to the study REDCap site. Parents will also be given the option to meet with study staff via videocall to orient the parent to the REDCap and/or study site and provide technical support. The study REDCap site opens with the study information sheet that provides contact details for study personnel. Participants who choose to participate will indicate consent by clicking a button at the bottom of the REDCap information sheet that reads, “YES, I acknowledge that I have viewed the information sheet and am voluntarily choosing to participate in this study.” Participants who click “YES” will then begin the baseline questionnaires. Participants who choose not to participate will click the “NO, I acknowledge that I have viewed the information sheet and I do not wish to participate in this study,” and they will receive a notification thanking them for their time and they will not be able to access the questionnaires.

After baseline measures have been completed, the predetermined randomization sequence will be used to randomize caregivers into one of the two conditions (R2R-TBI vs. IRC). Stratified randomization will be used to achieve balance in child’s age (< 5 years; ≥ 5 years) and injury severity. The randomization sequence will be based on a design with blocks of four or six chosen randomly within the sequence with equal probability. A pseudorandom number generator in R will be used, and the randomization sequence will be maintained by the statistician. Randomly varying block size reduces the chance that research staff will guess the next group assignment, minimizing unconscious bias. Block randomization with randomly mixed block sizes will then be performed with equal probabilities of assigning a participant to one of the two intervention groups.

4. Study Procedures

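### The randomisation strata (child's age, injury severity) are not named in the hypothesis 1 and 2 models; if they predict follow-up beyond baseline, the tests are slightly conservative

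*Combined protocol and SAP*

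**What the plan says.** Section 3.5 of the combined protocol and SAP states: "Stratified randomization will be used to achieve balance in" child's age, split at 5 years, and injury severity. Blocks of four or six are mixed at random and allocation is 1:1. The severity categories are not listed.

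Section 5.1 sets the outcome hierarchy: "Caregiver functioning is examined as the primary and most proximal outcomes", with "secondary outcomes of child recovery and family functioning" after it. Hypothesis 1 compares the groups "at one and six-months post-baseline, controlling for baseline scores". Hypothesis 2 does so "after controlling for baseline functioning". The analytic plan for both specifies "linear mixed-effect models used to examine changes in caregiver, family, and child functioning" from baseline to 6 months, with the one-month data added in a repeated-measures model. No list of fixed effects is given, and neither age nor severity is mentioned.

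The only other covariate rule for these models is in the attrition paragraph: "Factors related to dropout will be included as covariates in the analysis".

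**The concern.** Balancing the arms on age and severity removes between-stratum variation from the real sampling variability of the group difference. A model that omits the strata leaves that variation in its residual, so the SE it reports is larger than the estimate's true SE. The test then rejects less often than its nominal level and loses some power.

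The dropout rule does not settle this. It would admit a stratum only if that factor turned out to be associated with dropout, which is not pre-specification. Enrolment is capped at 200 and the documents give no power calculation, so no stated margin exists to absorb lost precision.

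**Working it through.** The plan gives no significance level, power, effect size, baseline correlation or strata effect, so there is no figure to reproduce.

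**From the documents:** up to 200 participants, 1:1 allocation, stratified blocks, adjustment for baseline.

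**Assumed:**
- two-sided 5% test; 80% power with the strata in the model; complete data;
- total outcome variance 1;
- strata explaining a share R² of total variance, with the same shift at baseline and follow-up;
- total baseline-to-follow-up correlation ρ.

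**Residual variances**
- Reported, baseline only: 1 − ρ²
- True, strata omitted but randomisation stratified: 1 − ρ² − R²(1 − ρ)²
- Strata in the model: (1 − R²) − (ρ − R²)²/(1 − R²)

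**Worked case, R² = 0.20, ρ = 0.4**
- Reported: 1 − 0.16 = 0.84
- True: 0.84 − 0.20 × 0.36 = 0.768
- Strata-adjusted: 0.80 − 0.04/0.80 = 0.75
- Reported SE over true SE: √(0.84/0.768) = 1.0458
- Reported SE over strata-adjusted SE: √(0.84/0.75) = 1.0583
- True SE over strata-adjusted SE: √(0.768/0.75) = 1.0119
- Type I error: 2[1 − Φ(1.960 × 1.0458)] = 0.0404
- Power: 80% with strata means an effect of 1.960 + 0.842 = 2.802 strata-adjusted SEs. Without strata, power is Φ[(2.802 − 1.960 × 1.0583)/1.0119] = Φ(0.719) = 76.4%
- Equivalent sample size with strata: 200 × [(1.960 + 0.719)/2.802]² ≈ 182.8, a loss of about 17

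| R² | ρ | Reported / true SE | Reported / strata-adjusted SE | Type I error | Power | Participants lost of 200 |
|---|---|---|---|---|---|---|
| 0.02 | 0.7 | 1.0018 | 1.0018 | 0.0496 | 79.9% | 0.5 |
| 0.02 | 0.4 | 1.0043 | 1.0044 | 0.0490 | 79.8% | 1.2 |
| 0.05 | 0.7 | 1.0044 | 1.0047 | 0.0490 | 79.7% | 1.3 |
| 0.05 | 0.4 | 1.0109 | 1.0115 | 0.0476 | 79.4% | 3.3 |
| 0.10 | 0.7 | 1.0089 | 1.0100 | 0.0480 | 79.4% | 2.9 |
| 0.10 | 0.4 | 1.0221 | 1.0247 | 0.0451 | 78.6% | 7.1 |
| 0.20 | 0.7 | 1.0181 | 1.0228 | 0.0460 | 78.6% | 6.9 |
| 0.20 | 0.4 | 1.0458 | 1.0583 | 0.0404 | 76.4% | 17.2 |

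**Simulation check.** In the last case (24,000 trials, stratified blocks of four or six, 2 × 3 strata), power was 75.8% without strata and 79.6% with them. With strata at N = 183 it was 75.6%. Type I error was 4.2% without strata and 5.1% with them.

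**Sensitivity to the equal-shift assumption.** If the strata move follow-up but not baseline, and explain a share S of the variance left after baseline, reported over true SE is 1/√(1 − S). For S = 5% and 10% that is 1.026 and 1.054, with type I error 4.4% and 3.9%. S is a share of post-baseline variance, so it is not on the same scale as R².

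**The case against.** **Size.** The largest loss comes from one corner of the grid. Nothing in the documents suggests that an age split and a severity grouping explain 20% of the variance in caregiver self-report. At 5% the cost is 1 to 3 participants. This stands.

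**Prognostic value.** Section 1.1 names greater severity and younger age as risk factors in a paragraph on child recovery. A reader might carry that over to caregiver depression, anxiety or self-efficacy. The documents do not make that link, so they support it at most for the secondary child outcome, and without an effect size. This stands.

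**Precision.** A reader might infer that stratification yields no precision unless the model contains the strata. That is wrong. In the worked case it already cuts the true variance from 0.84 to 0.768, against 0.75 with strata in the model. What is mainly lost is credit for the gain in the reported SE.

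**Change wording.** The model paragraph speaks of changes. In an unconstrained change contrast an equal strata shift cancels, and omitting the strata costs nothing. A reader might also infer from that wording that baseline adjustment is dropped, which would widen the SE by √(2/(1 + ρ)), or 8-20% for ρ of 0.7-0.4. Hypotheses 1 and 2 both commit to controlling for baseline, so the text does not support that reading. It is a separate matter and adds nothing to the loss here.

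**Silence is not exclusion.** The models have no covariate list, so the strata are unspecified, not ruled out. This is fair, and it is why the remedy is one clarifying sentence.

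**Conclusion.** The omission is in the text, and its direction is clear: if the strata predict follow-up beyond baseline, the baseline-adjusted tests for hypotheses 1 and 2 are conservative. There is no bias and no inflation of false positives, and a reader should not infer either.

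For R² of 5-20% and ρ of 0.7-0.4, the reported SE is 0.4-4.6% above the true SE and 0.5-5.8% above the strata-adjusted SE. Type I error is 4.9-4.0% and power 79.7-76.4% in place of 80%. At R² of 2% the loss is negligible. These figures rest on assumed inputs, an equal strata shift at both times and complete data, so they illustrate the size and do not bound it. This is a minor improvement worth making because it costs almost nothing, not a threat to the trial's conclusions.

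**What to change.** Add one sentence to the analytic plan for hypotheses 1 and 2: the mixed models include age stratum and injury-severity stratum as fixed effects, with the same categories as the randomisation list, alongside the baseline score to which the hypotheses already commit. Write out the severity categories there, since section 3.5 does not give them.

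Both factors are known at randomisation, so no new data are needed. The cost is 2 degrees of freedom if severity has two levels (1 for age, 1 for severity) or 3 if it has three (1 + 2). If the strata turn out not to be prognostic, almost nothing is lost: in simulation at N = 200 (8,000 trials), power was 79.6% with the strata and 79.7% without.

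### As most naturally read, the primary model omits the one-month scores; if so, 6-month dropout that depends on one-month status differently by arm can bias the primary effect

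*Combined protocol and SAP*

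**What the plan says.** The analytic plan for hypotheses 1 and 2 (section 5.1) opens: "The primary analysis will consist of a linear mixed-effect models used to examine changes in caregiver, family, and child functioning", compared between the arms "from baseline to 6-months post-baseline". The next sentence reads: "In addition, the one-month data will be included in a mixed model repeated measures analysis". The one after it claims the missing-data benefit: "This model allows for flexible modeling of the pattern of change in outcomes over time and uses all the data for a given participant".

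Three other statements bear on this:

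- Section 3.1 schedules measurement at baseline, one month and six months.
- Hypotheses 1 and 2 are to be judged at both follow-ups. For Hypothesis 1 the plan expects IRC caregivers to report "increasing levels of depression and distress at both one and six-month follow-ups" while R2R-TBI caregivers stay stable, so a group difference is expected by one month.
- Dropouts are to be compared with those who stay on background and on outcomes recorded before they left, and then: "Factors related to dropout will be included as covariates in the analysis". The plan does not say which analysis, or whether a one-month score could be such a covariate.

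The documents give no dropout rate, no missing-data assumption for the primary model and no sensitivity analysis for missing data.

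**The concern.** If the one-month scores were already in the primary model, the sentence beginning with an addition would have nothing to add. The claim to use every participant's data follows that sentence, so it appears to belong to the additional model. On that reading a caregiver who misses six months enters the primary model through baseline alone and says almost nothing about the treatment contrast.

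Dropout that depends on the one-month score is missing at random when that score is in the likelihood, and generally not when it is left out. Arm-specific dependence is plausible. R2R-TBI offers ten modules with weekly reminders, and IRC offers links. A caregiver who is still distressed at one month might give up on R2R-TBI, while one who has recovered might see no reason to continue in IRC. The primary estimate would then lean towards R2R-TBI, while the model that could correct it is supplementary.

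Two further consequences follow. A model of baseline and six months alone gives no one-month contrast, although both hypotheses call for one. The plan would also hold two estimates of the same 6-month effect.

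**Working it through.** The plan states no power, effect size, SD, correlation, alpha or dropout rate, so it has no figure to reproduce. The check is by algebra and simulation.

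**Inputs from the documents:** three visits (3.1); up to 200 participants and equal allocation (3.5).

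**Assumed:** SD 1; correlations 0.6 (baseline to 1 month), 0.6 (1 to 6 months) and 0.5 (baseline to 6 months); about 25% missing at six months in each arm; two-sided 5% test; dropout logistic in one-month distress; a one-month score observed for everyone who misses six months.

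**Step 1: source of the bias.** The slope of the 6-month score on the one-month score, given baseline, is b = (r16 − r01·r06)/(1 − r01²) = (0.6 − 0.6 × 0.5)/(1 − 0.36) = 0.30/0.64 = 0.469. Suppose that, among caregivers seen at six months, selection makes the arms differ by D in mean one-month score given baseline. With no true effect, a model without that score has bias b × D. If selection is the same in both arms, D = 0.

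**Step 2: size under no effect** (6000 simulated trials per scenario).

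| Dropout log-odds per SD of one-month distress | Two-visit bias | Two-visit type I error |
|---|---|---|
| +0.8 R2R-TBI, −0.8 IRC | 0.115 SD towards R2R-TBI | 12.7% |
| +0.5, −0.5 | 0.07 SD | 8.0% |
| 0.8 in one arm only | 0.06 SD | 6.8% |
| +0.8 in both arms | 0.00 SD | 5.0% |

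Repeat simulations of the first three rows gave 0.11 SD and 12 to 12.5%; 0.07 SD and 7.9 to 8.5%; 0.05 to 0.055 SD and 6 to 6.7%. The three-visit model was unbiased in those rows, with type I error of 4.5 to 5.3%. A two-visit mixed model that keeps the dropouts' baselines had the same bias as a completer analysis (0.114, 0.073 and 0.056 SD).

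**Step 3: check of the error rates.** With a two-visit SE of 0.142, the first row shifts the test statistic by 0.115/0.142 = 0.81. The rejection rate is Φ(−1.96 + 0.81) + Φ(−1.96 − 0.81) = 0.1251 + 0.0028 = 0.128. For one-arm dependence, 0.056/0.142 = 0.39 gives 0.0582 + 0.0094 = 0.068. Both agree with the table.

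**Step 4: with a true effect** of −0.30 at one month and −0.40 at six months (N = 200, 25% dropout).

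- Unrelated dropout: two-visit mean −0.402.
- Log-odds 0.5 in both arms: −0.397.
- Log-odds 1 in one arm only: −0.323.
- Log-odds 1 and −0.5: −0.298.
- Three-visit model: −0.397 to −0.404 throughout.

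Across a wider grid (dropout 20% or 35%; correlations also 0.7, 0.8 and 0.6 in the order above), equal dependence gave at most about 0.02 SD. One-arm dependence gave 0.06 to 0.13 SD, in either direction according to the arm.

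**Step 5: the planned covariate step.** Baseline factors remove only the part of dropout that they predict. The one-month score as a covariate adjusts away effect already present at one month: −0.40 + 0.469 × 0.30 = −0.40 + 0.141 = −0.259. With the higher correlations b = (0.8 − 0.7 × 0.6)/(1 − 0.49) = 0.38/0.51 = 0.745, and −0.40 + 0.745 × 0.30 = −0.176. Simulation gave about −0.26 and −0.18, even with no informative dropout.

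**Step 6: cost and limit of the three-visit model.** With unrelated dropout its SE is 0.139 against 0.142, about 2% smaller. Under the ±0.8 mechanism, if half of those missing six months also miss one month, about 0.05 SD of bias remains. At 80% it is 0.08 SD. At 100% it is 0.11 SD, the same as the two-visit model.

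**The case against.** A reader might infer that the plan definitely shuts the one-month data out of its primary model. It does not say so. The stated span can contain the one-month visit, a repeated-measures mixed model is itself a linear mixed model, and the sentence about using all the data may describe one combined model. This stands: the two-model reading is the more natural one, not a certain one.

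A reader might also infer that any dropout linked to one-month status biases the primary effect. The table refutes that. The dependence must differ by arm, and the documents do not show that it will. They give some reasons for restraint: both follow-up questionnaires are paid in both arms (9.1), staff check in with participants (4.1.4), and families may stop the modules yet stay in follow-up (4.1.6.2). Abandoning the website is therefore not the same as missing the 6-month survey. The 12% figure is the most adverse case shown and needs equal and opposite dependence.

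Finally, the three-visit model looks unbiased in the table partly by construction, because every dropout was given a one-month score. It is not a general cure. Nor can one say that the correcting data are already in hand: the protocol is prospective and only schedules the visit.

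None of this defends leaving the choice of model open. If one model was meant, the text still allows two 6-month estimates to compete for the primary label.

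**Conclusion.** The point holds in conditional form. On the natural reading the one-month scores lie outside the primary model. If they do, dropout that depends on them differently by arm can bias the primary 6-month effect. On the assumed inputs the bias is about 0.05 to 0.06 SD with one-arm dependence, and up to about 0.11 SD when the dependence is equal and opposite. Against an SE of about 0.14 SD, that raises a nominal 5% error to about 6 to 7% and about 12%. Same-direction dependence of equal strength is harmless under no effect and nearly so otherwise. The planned dropout covariates are not a remedy. The documents supply none of the dropout rates, correlations or mechanisms, so these sizes illustrate the risk and do not forecast it. The change is worth making because it costs nothing and lost no precision in these simulations.

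**What to change.** In section 5.1, name one primary model for hypotheses 1 and 2: a likelihood-based model of the baseline, one-month and six-month scores, with group-by-visit terms and an unstructured covariance. Take the 6-month and 1-month R2R-TBI minus IRC contrasts from it. State that the one-month outcome is not to be used as a covariate, including under the step that adds factors related to dropout. Delete the model of baseline and six months alone, or label it a sensitivity analysis.

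This is a free improvement. The visits are scheduled and the repeated-measures model is already planned, so only wording changes. The text should also acknowledge the limit: the model corrects for one-month status only where that score was observed, and it does not address dropout that depends on unseen 6-month values. That would need a separate sensitivity analysis.
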